### Secondary outcomes

2. Measurement of IMR in patients with AS prior to intervention and 6 months after SAVR/TAVI.
  - a. Description of the range of IMR values in a cohort of patients with severe AS.
    - i. Do all patients with severe AS have high microvascular resistance as assessed by IMR?
    - ii. Does IMR change significantly 6 months after TAVI/SAVR? If there is a significant decrease in IMR then this indicates that microcirculatory function improves 6 months after aortic valve intervention.
3. Null hypothesis: the “corrected” FFR (at baseline; based on baseline IMR) does not correlate with the post-intervention FFR.
  - a. If the null hypothesis is upheld then a correction of FFR using baseline IMR does not improve the validity of FFR in patients with severe AS.
4. Null hypothesis: using IMR at baseline does not improve the ischemia prediction of FFR. Ischemia is measured by SPECT (Figure 2).
  - a. If the null hypothesis is upheld then IMR does not improve stratification of coronary ischemia based on FFR.

- b. If a significant proportion of patients with SPECT ischemia have a raised IMR this would support the hypothesis that IMR can be used to correct falsely high (negative) FFR measurements.
- 5. Comparison of the diagnostic performance of FFR and RFR with SPECT ischemia (and compare with findings of Yamanaka *et al*).
- 6. Reproducibility of the FFR, RFR and IMR

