## 9. STATISTICS AND ANALYSIS

### 9.1 Sample Size

The sample size for the ***primary objective*** (change in FFR after aortic valve intervention) is based on previous measurements of FFR in patients with aortic stenosis, where a standard deviation of the data was reported. An expected mean FFR of 0.82 with a standard deviation of 0.08 was used in the calculation. Fifty eight (58) patients with pre- and post-interventions catheterizations will be sufficient to detect a reduction in the FFR from 0.82 to 0.79 with an alpha level of 0.05 and power of 0.80. A total sample of 100 patients with baseline measurements of which 80 patients will undergo (T)AVR without revascularisation (20% will undergo revascularisation) and in this way are eligible for pre-and post-intervention catheterization will allow for a 25 % drop-out during the follow-up phase of the study. Missing values will predominantly be at random. Therefore, the primary endpoint will be assessed using complete case analysis. To account for missing values, the number of patients will be increased from 58 to 80 (since missing data will be excluded from analysis).

For the ***secondary objective*** (comparison of FFR versus RFR): approximately 10-20% will have left main CAD, triple vessel disease, prior myocardial infarction or tandem lesions and will not be eligible for SPECT. One Hundred patients with baseline measurements will allow a 20% drop-out to end up with 80 patients with both baseline SPECT and invasive measurements. Yamanaka *et al.* found that a sample of 80 patients was necessary to determine the optimal cutoff value of iFR for indicating myocardial ischemia. Since RFR and iFR have an extremely high correlation (0.99), the same number of patients (80) is expected to achieve an area under the ROC curve of 0.70 with 0.90% power at a significance level of 0.05 in a 2-sided test.

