### 9.2 Statistical analysis

All quantitative variables will be tested for normal distribution according to the Kolmogorov-Smirnov test. Statistical analyses will be performed via the SPSS statistical software package,

applying a significance level of  $\leq 0.05$ . Continuous variables will be expressed as mean  $\pm$  SD. Comparisons will be done with paired t-, Wilcoxon rank signed, Mann-Whitney U- or Kruskal-Wallis test when appropriate. The chi-square test will be applied for categorical variables and results will be expressed as n (%). Analysis will be performed to compare the intra-coronary measurements (FFR, RFR, IMR) prior to intervention (group 1) versus 6 months after intervention (group 2). Descriptive statistics (mean/median, standard deviation and percentiles for continuous data; percentage for categorical data) and graphical representation (boxplots, histograms and density plots) will be used to compare both groups' characteristics. Intra-coronary measurements in both groups will then be compared and tested using statistical tests (paired t-, Wilcoxon rank signed test). The correlation between FFR and RFR will be analyzed using Pearson correlation coefficient. The diagnostic performance of RFR in indicating SPECT myocardial ischemia will be evaluated using receiver operating characteristic (ROC) curve analysis.

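### Item 4a reads a non-significant IMR result as proof of no added value, although the 80 SPECT patients were not sized for that question

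*Combined protocol and SAP*

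**What the plan says.** Study Objectives, Secondary outcomes, item 4 sets the hypothesis: "Null hypothesis: using IMR at baseline does not improve the ischemia prediction of FFR". Ischaemia is defined by SPECT. Item 4a gives the reading if the null is not rejected: "If the null hypothesis is upheld then IMR does not improve stratification of coronary ischemia based on FFR". Item 4b deals only with the positive reading.

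Section 9.1 gives the only sample size for the SPECT cohort, under the label "comparison of FFR versus RFR". It expects that "approximately 10-20% will have left main CAD, triple vessel disease, prior myocardial infarction or tandem lesions and will not be eligible for SPECT", and continues: "One Hundred patients with baseline measurements will allow a 20% drop-out to end up with 80 patients with both baseline SPECT and invasive measurements". The target is to "achieve an area under the ROC curve of 0.70 with 0.90% power at a significance level of 0.05 in a 2-sided test"; the power is evidently meant as 90%.

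Section 9.2 has one sentence on diagnostic performance: "The diagnostic performance of RFR in indicating SPECT myocardial ischemia will be evaluated using receiver operating characteristic (ROC) curve analysis". It names no model, test or estimate for IMR added to FFR. Item 4 of the secondary outcomes under Expected outcomes says only that IMR may help. It does not soften 4a.

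**The concern.** A non-significant test supports a conclusion of no effect only if the study had high power for the smallest effect that matters, or if the confidence interval excludes that effect. Item 4a requires neither. It is also worded more firmly than the primary rule 1a, which says only that an upheld null suggests FFR/RFR is valid.

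The protocol makes a combined FFR–IMR index a central question (Background) and describes a positive IMR finding as extremely important (Expected outcomes). If 4a is followed as written, a real but moderate contribution of IMR could be reported as absent, and the question closed on evidence that does not settle it.

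**Working it through.** **Inputs from the documents.** N = 100 × (1 − 0.20) = 80 with SPECT and invasive data; ROC area 0.70; two-sided alpha 0.05; power read as 90% (all Section 9.1).

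**Inputs not in the documents, assumed.** Null ROC area 0.50 for the plan's own figure; SPECT ischaemia prevalence 20–50%; FFR area 0.70 (the value in Section 9.1, stated there for a different purpose); IMR independent of FFR within ischaemia class; IMR effect as listed below; likelihood-ratio test of IMR added to FFR in a logistic model.

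**1. The plan's figure.** Hanley–McNeil variance with A = 0.70: Q₁ = A/(2 − A) = 0.538 and Q₂ = 2A²/(1 + A) = 0.576. With 40 ischaemic and 40 non-ischaemic patients:
- Variance under A = 0.70: [0.21 + 39(0.538 − 0.49) + 39(0.576 − 0.49)]/1600 ≈ 0.00342, SE 0.0585.
- Variance under A = 0.50: 81/(12 × 1600) = 0.00422, SE 0.0650.
- Power = Φ[(0.20 − 1.96 × 0.0650)/0.0585] ≈ 89%.

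So N = 80 reproduces at about 45–50% prevalence. At 30% the power is 82–85%, depending on the variance used. This calculation concerns one index against chance. It contains nothing about a second marker added to FFR.

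**2. Effect scale for IMR.** With normal markers, area = Φ(d/√2), so 0.70 means d = 0.742 for FFR. An independent IMR with standardised difference d₂ gives a combined d of √(0.742² + d₂²):
- d₂ = 0.5: √0.801 = 0.895, area 0.736 (gain 0.036).
- d₂ = 0.60: √0.911 = 0.954, area 0.750 (gain 0.05).

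**3. Probability of missing the effect at N = 80** (simulation, 1,500 runs per cell):

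| True IMR effect | Prevalence 20% | 30% | 50% |
|---|---|---|---|
| 0.5 SD (gain 0.036) | 60% | 51% | 46% |
| Gain 0.05 | 48% | 34% | 29% |

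Repeat runs moved single cells by up to about four points. With no IMR effect the test rejected in 4.5–5.6% of runs, so it is adequately calibrated. As a rough check, a two-sample t-test for 0.5 SD that ignores FFR has power 0.42, 0.53 and 0.60 at the three prevalences, slightly above the simulated power, as expected.

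**4. Dependence on the assumed effect.** Using odds ratios per SD of IMR, prevalence 30–50% and FFR area 0.70–0.80:

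| Odds ratio per SD | Miss rate at N = 80 | N for 80% power (prevalence 40%) |
|---|---|---|
| 1.5 | 61–69% | 251–299 |
| 1.75 | 38–48% | 144–170 |
| 2.0 | 22–36% | 102–121 |
| 2.5 | 6–17% | 69–82 |

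An FFR–IMR correlation of ±0.3 changes little (about 47% missed at odds ratio 1.75, FFR area 0.75, prevalence 40%). If all 100 patients had SPECT, about 30% would still be missed at odds ratio 1.75 (FFR area 0.70, prevalence 40%).

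**5. What a null estimate would exclude.** Ignoring FFR, the SE of the log odds ratio per SD near the null is 1/√[N·p(1 − p)]. At p = 0.5 this is 1/√20 = 0.224, so an observed odds ratio of exactly 1 has upper 95% limit exp(1.96 × 0.224) = 1.55. At p = 0.2 it is 1/√12.8 = 0.280, limit 1.73. Adjustment for FFR widens the interval. Even a perfectly null estimate would therefore not exclude an odds ratio of 1.5.

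**The case against.** The strongest reply is that 4a is one interpretive sentence for a secondary objective, in a single-centre cohort with no study intervention, and that the miss rates rest on an effect size, prevalence and test that the documents do not give. Both parts are fair. They limit the severity and make the percentages conditional. They do not rescue the rule, because no stated power or margin supports a negative conclusion under any assumed effect. The same construction appears in the primary rule 1a and in 3a, so one general sentence on non-significant results could cover all three.

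Three stronger readings are tempting and are not supported.

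- A reader might infer that, because ROC analysis is the only diagnostic method in Section 9.2, IMR would be judged by comparing two ROC areas, with a miss rate near 90%. The ROC sentence concerns RFR, and no such comparison is planned for IMR. The DeLong test on these nested models also rejects a true null only about 0.2–0.3% of the time, so much of that figure reflects a miscalibrated test and not the sample size.
- A reader might infer that a false negative is generally about as likely as a correct positive. That fits the 0.5-SD case only. At a gain of 0.05 and prevalence 30–50%, power is 66–71% against misses of 34–29%.
- A reader might infer that 4a declares IMR useless. Its wording is confined to stratification of ischaemia based on FFR.

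**Conclusion.** The point holds. Item 4a draws a definite negative conclusion from a non-significant result, and nothing elsewhere in the document gives power, a margin or a confidence limit to support it. That part needs no assumption.

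The size is conditional. With N = 80, FFR area 0.70, IMR independent of FFR, prevalence 20–50% and a likelihood-ratio test, roughly 30–50% of trials would miss a true gain of 0.05 in ROC area, and roughly 45–60% would miss a 0.5-SD IMR difference. For a large effect (odds ratio 2.5 per SD, area from about 0.70 to 0.79 when FFR alone gives 0.70) the rate falls to 6–17%. The assumed effect should always stand beside the percentage. The rule should be changed, but it concerns a secondary objective and leaves the primary analysis untouched.

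**What to change.** Replace item 4a with:

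> If adding IMR to FFR is not statistically significant (likelihood-ratio test for IMR in a logistic model of SPECT ischaemia that contains FFR), the result is inconclusive. The IMR odds ratio and the gain in AUC will be reported with 95% confidence intervals. A conclusion that IMR does not improve stratification will be drawn only if the confidence interval excludes a gain that the sponsor has specified and justified in advance.

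Add to Section 9.2 the logistic model, the likelihood-ratio test and the interval method. For the AUC gain, use a bootstrap interval corrected for optimism. The DeLong interval is unsuitable here: in simulation with a true gain of 0.05, its upper 95% limit fell below 0.05 in about 8–11% of trials, against a nominal 2.5%. The 0.05 is used only for illustration. The documents contain no basis for a margin, so the sponsor must choose and defend one.

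The cost is a reworded item and a short addition to Section 9.2, with no extra patients or measurements. The downside is that some results that would have been reported as negative become inconclusive.

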## 1. BACKGROUND

Aortic stenosis (AS) is the most common primary valve disease leading to surgery or catheter intervention in Europe, with a growing prevalence due to the aging population. Severe aortic valve stenosis, defined by a mean gradient over the aortic valve of greater than 40mmHg or an aortic valve area of less than 1.0cm^2, is associated with significant morbidity and mortality and is treated by surgical valve replacement (SAVR) or transcatheter aortic valve implantation (TAVI). However, significant coronary artery disease (CAD) is reported in more than 60% of patients with AS, and needs to be correctly assessed because untreated significant CAD is associated with adverse outcomes.

Current guidelines recommend intra-coronary pressure measurement using either fractional flow reserve (FFR) or non-hyperemic pressure ratios (NHPRs) for the assessment of intermediate coronary artery lesions before revascularization. A FFR of  $\leq 0.80$  or a NHPR of  $\leq 0.89$  is considered to indicate that a coronary lesion is significant. Non-hyperemic pressure ratios include the instantaneous wave-free ratio (iFR) and the resting full cycle ratio (RFR), which have been shown to be comparable. However, correctly identifying hemodynamically significant coronary stenoses is difficult in patients with AS because of the hypertrophic remodelling related to the valve pathology. Aortic stenosis is associated with a significant increase in left ventricular (LV) mass resulting in pathological changes in coronary and LV hemodynamics, which are associated with coronary microvascular dysfunction.

With the development of microvascular dysfunction, intra-coronary pressure measurements become less reliable and, currently, whether FFR, or the NHPRs, can reliably detect myocardial ischemia in patients with severe AS is controversial, making it difficult for physicians to correctly determine whether or not coronary lesions should be revascularized prior to TAVI or at the time of SAVR. Yamanaka *et al.* recently reported a strong correlation of iFR with FFR in patients with

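### Objective 4 asks whether IMR adds to FFR in predicting SPECT ischaemia, but criterion 4b looks only at SPECT-positive patients and section 9.2 assigns no analysis that could answer it

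*Combined protocol and SAP*

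**What the plan says.** In the study objectives, under Secondary outcomes, item 4 opens with a comparative hypothesis: "Null hypothesis: using IMR at baseline does not improve the ischemia prediction of FFR". SPECT is the reference standard and the reader is sent to Figure 2. Item 4a says what follows if that null stands. Item 4b gives the only stated route to a positive conclusion: "If a significant proportion of patients with SPECT ischemia have a raised IMR this would support the hypothesis that IMR can be used". The purpose it names for IMR is "to correct falsely high (negative) FFR measurements".

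Item 2.a.i of the same list asks an open question: "Do all patients with severe AS have high microvascular resistance as assessed by IMR".

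The Background gives numerical limits for FFR (0.80 or below) and for non-hyperaemic ratios (0.89 or below), each of which "is considered to indicate that a coronary lesion is significant". The available text gives no such limit for IMR.

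Section 9.1 sizes the SPECT work for the FFR versus RFR comparison: "One Hundred patients with baseline measurements will allow a 20% drop-out to end up with 80 patients with both baseline SPECT and invasive measurements". The target there is "an area under the ROC curve of 0.70 with 0.90% power at a significance level of 0.05 in a 2-sided test". Section 9.2 then says: "The diagnostic performance of RFR in indicating SPECT myocardial ischemia will be evaluated using receiver operating characteristic (ROC) curve analysis". It names IMR only in the comparison of values before and 6 months after valve intervention.

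**The concern.** The hypothesis and the criterion ask different questions. The hypothesis asks whether knowing IMR, on top of FFR, separates ischaemic from non-ischaemic patients better than FFR alone. That needs both kinds of patient. Criterion 4b uses only the ischaemic ones. A high share of raised IMR among them says nothing about discrimination unless the share among non-ischaemic patients is lower.

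There is a second mismatch. The conclusion drawn in 4b concerns FFR values that are falsely negative, yet the patients counted are not restricted to those with a negative FFR. A SPECT-positive patient whose FFR is already positive counts towards support, although there is no false negative to correct.

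Section 9.2 would normally settle which test decides the matter, and here it does not. The analyst is left with 4b, an undefined proportion and, in the available text, an undefined threshold. At stake is a secondary claim to which the Expected outcomes section attaches high importance and which it extends to other patient groups with microvascular dysfunction.

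**Working it through.** **Inputs from the documents.** The number with both SPECT and invasive baseline data is 80. It reproduces: 100 × (1 − 0.20) = 80 (section 9.1). No sample size, power or threshold is given for objective 4 itself; the AUC target in 9.1 belongs to the RFR question.

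**Inputs not in the documents, so assumed.**
- SPECT-positive share: 35%, so m = 0.35 × 80 = 28 patients. Range checked: 30% to 50%, or 24 to 40 patients.
- Prevalence q of raised IMR in the cohort: 30% to 90%. Item 2.a.i leaves open that it is 100%.
- Meaning of the proportion in 4b: at least half as the main reading, with a looser and a stricter reading alongside.

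**Step 1: what 4b measures if IMR is uninformative.** Under independence, P(raised IMR | SPECT-positive) = P(raised IMR) = q. The 4b proportion therefore estimates cohort prevalence. If the answer to item 2.a.i were yes (q = 1), all SPECT-positive patients would have raised IMR. 4b would be met with certainty although IMR, as a raised/not-raised marker, could not discriminate at all.

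**Step 2: chance of false support.** With X ~ Bin(28, q) the three readings are:
- at least one third: X ≥ 10;
- at least half: X ≥ 14;
- significantly above 50%: X ≥ 20, the smallest count whose exact upper tail under q = 0.5 is at most 0.025 (it is 0.018).

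| q | X ≥ 10 | X ≥ 14 | X ≥ 20 |
|---|---|---|---|
| 30% | 0.32 | 0.02 | <0.001 |
| 50% | 0.96 | 0.57 | 0.02 |
| 70% | >0.999 | 0.992 | 0.53 |
| 80% | >0.999 | 0.9999 | 0.91 |

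Varying m from 24 to 40 changes the at-least-half figures little: 0.01 to 0.03 at 30%, 0.56 to 0.58 at 50%, and 0.99 or more at 70%. Under the strict reading the 70% figure runs from 0.39 to 0.70.

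**Step 3: the same data with a comparison group.** Compare the raised-IMR proportion in SPECT-positive and SPECT-negative patients (80 in total), again with IMR independent of ischaemia. By exact enumeration over q = 30% to 90% and m = 24 to 40, a two-sided chi-square test at 0.05 gives false support in 4.5% to 5.9% of trials. Fisher's exact test gives 1.7% to 4.0%. The error no longer depends materially on prevalence. This contrast still does not test added value over FFR; it only shows what the missing comparator does.

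**Step 4: what 80 patients can detect.** Normal-approximation power for that two-group contrast, over the same range of m, is 37% to 45% for 70% versus 50% raised, and 73% to 82% for 80% versus 50%. An analysis confined to FFR-negative patients would use fewer than 80 and have less power for the same difference.

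**The case against.** The strongest reply is that 4b is an interpretive remark and that the hypothesis of objective 4, stated just above it, is properly comparative. That is right. A reader might infer that 4b is the decision rule for the whole objective, or that the plan never frames the question as added value over FFR. The text does not support either: the parent null is the formal hypothesis, and the importance claimed under Expected outcomes attaches to IMR improving prediction, not to the 4b proportion. What remains is that no analysis is assigned to that null, so 4b is the only stated criterion for a positive answer.

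A reader might also infer that the plan contains no IMR cut-off. This cannot be concluded. Figure 2 illustrates this objective and is not shown; its legend gives no value, but the figure might. A cut-off there would remove the freedom to choose one afterwards, but would not by itself create a test of added value.

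Third, false support is not inevitable. The high figures require raised IMR to be common, which the documents do not state. Item 2.a.i is a question, and the Background speaks of microvascular dysfunction being present or absent. At 30% prevalence, with the half or strict reading, the risk is small.

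Finally, objective 2a will describe IMR across the cohort, and 9.2 lists chi-square and Mann-Whitney tests that could compare IMR by SPECT status. Both help, but neither test is tied to that comparison, and neither would show what IMR adds to FFR.

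**Conclusion.** The concern stands as a mismatch between hypothesis, criterion and analysis. Objective 4 poses a comparative question, 4b answers a different one, and 9.2 assigns no analysis to either. Under 4b an uninformative IMR can appear to support correcting FFR, with a probability set by background prevalence and by how the criterion is read. With 28 of 80 SPECT-positive and the at-least-half reading, that probability runs from about 0.02 at 30% prevalence to 0.9999 at 80%. All three inputs (SPECT-positive share, prevalence, reading) are assumptions. The logical point that the proportion equals prevalence under independence needs none of them. No printed figure in the plan is shown to be wrong. Because the objective is secondary and the remedy simple, this should be corrected, but it does not threaten the primary analysis.

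**What to change.** 1. Reword 4b so that support for IMR rests on rejecting the parent null of objective 4, not on a proportion within SPECT-positive patients.
2. Add to 9.2, for all patients with SPECT: a logistic model of SPECT ischaemia on continuous FFR, then on continuous FFR plus continuous IMR. Report the likelihood-ratio test for IMR and the change in AUC with its confidence interval.
3. Report IMR by SPECT status within FFR-negative patients as descriptive only, because that subset is small.
4. If an IMR cut-off is used for description, state it, or point to Figure 2 if it is there, before SPECT results are merged with the invasive data.

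FFR, IMR and SPECT are all scheduled at baseline, so no new visit or measurement is needed. The cost is a rewording and slightly more analysis work. The limitation to acknowledge is power: with about 80 patients a modest IMR effect may be missed, so a non-significant result should be read through the confidence interval and not as proof that IMR adds nothing.
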